**Table 11. Criteria for the Assessment of the Disease Activity of DAS28**

Evaluation index	Remission	Low disease activity	Moderate disease activity	High disease activity
DAS28	<2.6	≥2.6 to <3.2	≥3.2 to ≤5.1	>5.1

- EULAR response of DAS28**

The proportion of EULAR response at each time point for DAS28 will be calculated.

As for each time point, “Appendix 11.1.1 Definition of Visit Timing” will be followed.

Also, the values with LOCF for "changes in DAS28" as described above should be used to calculate the remission at each assessment timepoint up to Month 6 of treatment, as well as the proportion of patients in remission and disease activity, as well as a 95% confidence interval for the proportion of patients in remission.

The subgroup analyses by the average actual daily dose will be calculated for the abouve analyses.

Criteria for the assessment of the response of DAS28 will be based on Table 12.

**Table 12. Criteria for the assessment of the response of DAS28**

Baseline DAS28	Response of DAS28		
	Response>1.2	0.6<Response≤1.2	Response≤0.6
DAS28≤3.2 Low disease activity	Good Response		
3.2<DAS28≤5.1 Moderate disease activity		Moderate Response	
DAS28>5.1 High disease activity			No response

- **Changes in TJC, SJC, patient VAS, physician VAS, CRP, and ESR**

Summary statistics will be calculated for the measurements of TJC, SJC, patient VAS, physician VAS, CRP, and ESR, which are used for the calculation of efficacy endpoints, at each time point, and the change from the initiation of administration of Xeljanz. For the change, 95% confidence intervals will be calculated.

As for each time point, “Appendix 11.1.1 Definition of Visit Timing” will be followed.

Furthermore, summary statistics of measurements, the change will be calculated at each time point up to Month 6 will be calculated with imputation by LOCF (Section 7) for missin data (ie, no data within the acceptable window for a visit in 11.1.1)

The subgroup analyses by the average actual daily dose will be calculated for the abouve analyses.

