## 2 Subjects

Among rheumatoid arthritis patients with poorly controlled disease in spite of continuous use of a methotrexate preparation (hereinafter, MTX) in a dosage exceeding 8 mg/week for 3 months or more, those meeting the following criteria:

- 1) All patients who receive Xeljanz (Xeljanz group)
- 2) Patients who have begun pharmacotherapy with another drug\* (control group)

\*Patients with no experience of treatment with Xeljanz (Patients participating in clinical trial cannot be registered in the control group)

When using Xeljanz, refer to “Guidelines for the use of tofacitinib in all-cases post-marketing surveillance” (revised version on June 29, 2014) (Japan College of Rheumatology) (hereinafter, “tofacitinib use guidelines”). Please consider using a pharmacotherapy other than Xeljanz for patients who do not meet the criteria shown below.

[Target patients]

1. Rheumatoid arthritis patients with poorly controlled disease in spite of continuous use of a methotrexate preparation (MTX) in a dosage exceeding 8 mg/week for 3 months or more. Patients with the above treatment history after February 23, 2011 when the approved dosage for MTX was increased to 16 mg/week are targeted. However, it is desirable not to target patients to whom MTX cannot be administered from the safety perspectives at this point, in principle.
  - Painful joint count of 6 or more
  - Swollen joint count of 6 or more
  - CRP of 2.0 mg/dL or more or ESR of 28 mm/hr or more
 Even if patient does not meet the 3 criteria above, consider use if there is moderate or higher activity for any of
  - DAS28-ESR, SDAI, and CDAI.
2. Moreover, out of consideration for safety with respect to opportunistic infections, it is strongly recommended that the following 3 criteria be met.
  - Peripheral blood count of 4000/mm^3 or more
  - Peripheral lymphocyte count of 1000/mm^3 or more
  - Negative for blood β-D-glucan

Excerpted from “tofacitinib use guidelines”

The indication and dose regimen for this Surveillance are as follows: (This surveillance targets rheumatoid arthritis patients with poorly controlled disease in spite of continuous use of a methotrexate preparation (MTX) in a dosage exceeding 8 mg/week for 3 months or more.)

- Indication: Patients with rheumatoid arthritis who showed inadequate response to conventional treatments
- Dosage and Administration: As a standard therapy, a patient should receive a daily oral administration of tofacitinib 5 mg BID.

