#### **8.2.4.2. DAS28**

- Changes in DAS28**

Summary statistics for the measurement of DAS28(4/ESR) at each time point and the change from the initiation of administration of Xeljanz will be calculated. For the change, 95% confidence intervals will be calculated.

As for each time point, “Appendix [11.1.1 Definition of Visit Timing](#)” will be followed.

Furthermore, summary statistics of measurements, the change will be calculated at each time point up to Month 6 will be calculated with imputation by LOCF ([Section 7](#)) for missin data (ie, no data within the acceptable window for a visit in Appendix [11.1.1](#))

The subgroup analyses by the average actual daily dose will be calculated for the abouve analyses.

- Disease activity of DAS28**

The proportion of remission and disease activity at each time point for DAS28(4/ESR) and the 95% confidence interval for the proportion of remission will be calculated.

As for each time point, “Appendix [11.1.1 Definition of Visit Timing](#)” will be followed.

Also, the values with LOCF for "changes in DAS28" as described above should be used to calculate the remission at each assessment timepoint up to Month 6 of treatment, as well as the proportion of patients in remission and disease activity, as well as a 95% confidence interval for the proportion of patients in remission.

The subgroup analyses by the average actual daily dose will be calculated for the abouve analyses.

Criteria for the assessment of the remission and disease activity of DAS28(4/ESR) will be based on Table 11.

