## Ordinal Scale

Item	Category	Note
Initial daily dose of Xeljanz [ mg ]	5 mg, 10 mg, >10 mg	Reference: 5mg
Lymphocyte count [ /mm  ]	<500, ≥500 to <1000, ≥1000	Reference: <500
Status of MTX use (Dose prior to the start date of survey 1)	Absent, >0 mg to ≤8 mg/week, >8 mg/week	Reference: absent
Status of MTX use (Dose prior to the start date of survey 2)	Absent, >0 mg to ≤2 mg/week, >2 mg to ≤4 mg/week, >4 mg to ≤6 mg/week, >6 mg to ≤8 mg/week, >8 mg to ≤10 mg/week, >10 mg to ≤12 mg/week, >12 mg to ≤14 mg/week, >14 mg to ≤16 mg/week, >16mg/week	Reference: absent
	≤3.3, >3.3 to ≤11, >11 to ≤26, >26	Reference: ≤3.3
SDAI	≤11, >11 to ≤26, >26	Reference: ≤11
	≤2.8, >2.8 to ≤10, >10 to ≤22, >22	Reference: ≤2.8
CDAI	≤10, >10 to ≤22, >22	Reference: ≤10
	<2.6, ≥2.6 to <3.2, ≥3.2 to ≤5.1, >5.1	Reference: <2.6
DAS28	<3.2, ≥3.2 to ≤5.1, >5.1	Reference: <3.2

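### SAP Table 12 picks the EULAR response row by baseline DAS28, so as printed a patient starting above 3.2 appears unable to be a Good responder

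*SAP*

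**What the plan says.** In SAP Section 8.2.4.2, the item on EULAR response states: "The proportion of EULAR response at each time point for DAS28 will be calculated". It then gives the rule: "Criteria for the assessment of the response of DAS28 will be based on Table 12".

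Table 12 is a three-by-three grid. Its rows are headed "Baseline DAS28" and split at 3.2 and 5.1; the first row is labelled "DAS28≤3.2 Low disease activity". Its columns are Response above 1.2, above 0.6 up to 1.2, and 0.6 or less. Three labels can be read: Good in the first row and first column, Moderate in the second row and second column, and No response in the third row and third column.

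Response itself is not defined. The nearest text, under changes in DAS28, says only that "the change from the initiation of administration of Xeljanz will be calculated".

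Table 11, in the same section, classifies DAS28 at each time point and sets remission at below 2.6. Protocol Section 2 describes the target population as "rheumatoid arthritis patients with poorly controlled disease" despite methotrexate.

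**The concern.** Choosing the row by baseline DAS28 ties the best response category to patients who already had low disease activity at the start. In a survey of poorly controlled disease, those are the patients one would least expect to find. A patient who starts high and reaches remission would not be counted as Good.

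If the program follows the printed header, the EULAR response table and its subgroups by average actual daily dose (below 7.5 mg, and 7.5 mg or more) would show no Good response for anyone starting above 3.2. The DAS28 remission table beside it could count some of those same patients as in remission. If only the header is wrong and the program used the visit value, the results stand and only the SAP text needs correcting.

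**Working it through.** No sample size, power or test is involved. The check applies the two tables to the same patients.

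**Inputs.** Table 12: row cuts 3.2 and 5.1, column cuts 1.2 and 0.6, and the three visible labels. Table 11: remission below 2.6, high activity above 5.1. Let B be baseline DAS28, V the DAS28 at the visit, and Response = B − V. The SAP does not write this definition down, but the column layout implies it, since larger values lead to Good.

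**What Good requires as printed.** B ≤ 3.2 and B − V > 1.2. Hence V < B − 1.2 ≤ 3.2 − 1.2 = 2.0. A patient with B > 3.2 is never in the row where Good is visible, however large the fall.

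**Worked cases.**

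| B | V | B − V | Table 11 at visit | Table 12, row by baseline | Table 12, row by visit value |
|---|---|---|---|---|---|
| 6.0 | 2.4 | 3.6 | remission | row > 5.1, column > 1.2: no label visible | row ≤ 3.2, column > 1.2: Good |
| 5.0 | 2.4 | 2.6 | remission | middle row, column > 1.2: no label visible | row ≤ 3.2, column > 1.2: Good |
| 3.1 | 1.8 | 1.3 | remission | row ≤ 3.2, column > 1.2: Good | row ≤ 3.2, column > 1.2: Good |

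All three patients are in remission by Table 11. With the row set by baseline, only the one who started low is visibly Good. With the row set by the visit value, all three are.

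**Whether other text supplies the visit value.** The LOCF paragraph under EULAR response describes remission and disease activity, not the response categories. I found no other section that sets the Table 12 row by the DAS28 reached at the visit.

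**Side note.** Table 12 places exactly 3.2 in the low band. Table 11 and the DAS28 bands in SAP Appendices 11.1.2 to 11.1.4 ("<3.2, ≥3.2 to ≤5.1, >5.1") place it in the middle band. This concerns a single value of a nearly continuous score.

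**The case against.** The strongest reply is that nothing here is a formal contradiction. Table 11 classifies a state and Table 12 a response, and neither document says that a patient in remission must be a Good responder. The intended rule sits in SAP reference 1, which the documents do not reproduce. There are also cues that the header is only a slip: response is to be assessed at each time point, and the row labels (low, moderate, high disease activity) echo the Table 11 categories that are applied at each visit. All of this stands. It is why the row variable has to be confirmed and cannot be declared wrong, but it does not change what the header says.

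A reader might go further and infer that no patient starting above 3.2 can be Good. The documents do not fully support that. Six of the nine cells show no label in the text of the table, and merged cells may have been lost. The diagonal layout makes it unlikely that Good extends down the first column, but does not exclude it. Even then the baseline header would be awkward: 8.0 to 6.7 is a fall of 1.3 and would be Good, although 6.7 is still high activity by Table 11.

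A reader might also infer that the undefined Response could carry a negative sign and turn large improvements into No response. The column layout makes that implausible, because Good sits under the larger values.

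Finally, a reader might infer that most patients are affected. No baseline DAS28 distribution is given. The activity criteria in Protocol Section 2 are guideline advice, and moderate activity on SDAI or CDAI alone is enough, so some patients may start at or below 3.2. The share is unknown.

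**Conclusion.** The point holds as a defect in a stated classification rule. Table 12 selects its row by baseline DAS28, and programmed that way it appears to withhold Good from patients who start above 3.2 and reach remission. This rests on two conditions: that the visible position of the Good label reflects the full extent of its cell, and that reference 1 sets the row by the DAS28 attained. Neither can be settled from the documents.

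The impact is minor. EULAR response is a descriptive tabulation in the Xeljanz group only, with no test and no confidence interval specified for the response proportion. It is not among the endpoints in SAP Section 6.2, and the protocol's primary effectiveness analysis is change in SDAI and DAS28 (Protocol Section 8.3). DAS28 change, DAS28 remission, the tested SDAI remission subgroups and all comparisons with the control group are unaffected.

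**What to change.** - Check the row header of Table 12 against SAP reference 1. If confirmed, relabel the rows as DAS28 at the assessment time point.
- State that Response is baseline DAS28 minus visit DAS28.
- Check in the PDF how far each response cell extends, and label all nine cells explicitly.
- Optionally, note which band holds exactly 3.2 and whether the difference from Table 11 is deliberate.
- Check which DAS28 value the program used to pick the row. Rerun the EULAR response table and its dose subgroups only if it was baseline.

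The cost is one header checked against a cited source, one definition and one program check. At most, one descriptive table and its dose subgroups are rerun.

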#### **8.2.4.3. Subgroup analysis**

For the following endpoint, an analysis will be performed for each of the subgroups specified in Section 5.4.

- Number and proportion of patients achieving SDAI remission after 6 months from initiated xeljanz administration

In addition, statistical tests will be performed between the levels of factors in accordance with [Section 8.1.3](#). At the tests, unknown, unspecified, and unmeasured data will be excluded from the analysis.

CCI

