## 1 Objective

The objective of this Surveillance is to verify the following subject matters concerning Xeljanz® Tablets (hereinafter referred to as “Xeljanz”) under post-marketing actual status of use.

- 1) Occurrence of adverse reactions, factors that may potentially affect safety, and effectiveness
- 2) Long-term safety (particularly, malignant tumors and serious infections) and effectiveness

Occurrences of malignant tumors and serious infections will be compared with a control group.

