#### **8.1.3. Analysis of Binary Data**

Frequency and the proportion will be calculated. If a confidence interval for proportion is calculated, a 2-sided 95% confidence interval will be calculated. At the tests, unknown, unspecified, and unmeasured data will be excluded from the analysis.

If a test is performed, Fisher's exact test will be performed for a relationship with nominal scale data and Cochran-Armitage test (exact method) will be performed for a relationship with ordinal scale data.

Ratios and differences of proportions and their 95% confidence intervals will be calculated to compare proportions among treatment groups.

Risk ratios and their 95% confidence intervals will be calculated to compare proportions among subgroups.

If a model analysis is performed, a logistic regression model will be used.

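### The visible plan tests effectiveness factors on Month-6 SDAI remission without adjusting for baseline SDAI, so a factor can be flagged only because it marks lower starting activity, or missed because of higher starting activity

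*SAP*

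**What the plan says.** SAP 8.2.4.3 (Subgroup analysis) names a single endpoint for the effectiveness factors: "Number and proportion of patients achieving SDAI remission after 6 months from initiated xeljanz administration". Table 10 defines SDAI remission as 3.3 or below. The factors are those of Section 5.4, which brings in Appendix 11.1.4 (age, weight, BMI, stage, functional class, disease duration, prior biologics, MTX dose, baseline SDAI, CDAI, DAS28 and others).

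The section then orders testing: "In addition, statistical tests will be performed between the levels of factors in accordance with" Section 8.1.3. That section supplies two tests. For nominal factors, "Fisher's exact test will be performed for a relationship with nominal scale data". For ordinal factors, "Cochran-Armitage test (exact method) will be performed for a relationship with ordinal scale data". Neither takes a covariate. A regression appears only conditionally: "If a model analysis is performed, a logistic regression model will be used". The visible text of 8.2.4.3 does not call for one and names no covariates.

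The efficacy analysis sets in 5.2 do not exclude patients who start in remission. Appendix 11.1.4 provides for them: baseline SDAI is a tested factor with levels "≤3.3, >3.3 to ≤11, >11 to ≤26, >26", and the lowest level is the reference.

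**The concern.** The endpoint is a state at Month 6, not a change from the start. Suppose every patient improves by the same proportion. Those who began nearer 3.3 cross it more often, and any factor that tracks starting activity then shows different remission proportions. Stage, functional class and prior biologic use could plausibly be such factors, and baseline CDAI and DAS28 share components with SDAI. For baseline SDAI itself, the test relates a measurement to its own later value.

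The reverse can also happen: a level whose patients respond better but start with more active disease can look no different. What is at stake is how the factor table is read. A small p-value could be taken to mean that a kind of patient responds better when it shows only that such patients start milder, and a large one could hide a real difference.

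**Working it through.** **Figures in the plan.** The documents give no rate, power or sample size for these tests, so there is no planning figure to reproduce. They also give no baseline SDAI distribution. The inputs below are assumptions except the cut-off (Table 10) and the two-sided 5% level (SAP Section 4).

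**Assumed inputs, main scenario.** 2500 patients; factor present in 30% (750 against 1750); baseline SDAI log-normal with median 22 and log-SD 0.6; Month-6 SDAI = baseline × 0.40 × log-normal noise with log-SD 0.8, the same for everyone. The factor has no effect on relative response. It only raises baseline log-SDAI by d SDs.

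**Step 1: remission proportions.** Month-6 log-SDAI has SD √(0.6² + 0.8²) = 1.0, so

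P(remission) = Φ[ln 3.3 − ln(22 × 0.40) − 0.6d] = Φ[−0.981 − 0.6d].

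Without the factor this is Φ(−0.981) = 0.163. With it:

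| d (SD) | P(remission) | Ratio to 0.163 |
|---|---|---|
| 0.1 | 0.149 | 0.91 |
| 0.2 | 0.135 | 0.83 |
| 0.3 | 0.123 | 0.75 |
| 0.5 | 0.100 | 0.61 |

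**Step 2: how often the planned test rejects.** Normal approximation at d = 0.3: difference 0.163 − 0.123 = 0.0405; standard error √(0.123 × 0.877/750 + 0.163 × 0.837/1750) = 0.0149; z = 2.72; rejection about Φ(2.72 − 1.96) = 78%. The same formula gives 15%, 44% and 99% at d = 0.1, 0.2 and 0.5.

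**Step 3: simulation, 500 data sets per setting.**

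| d (SD) | Fisher, as planned | Logistic with log baseline SDAI |
|---|---|---|
| 0 | 4.8% | 4.0% |
| 0.1 | 14.4% | 4.8% |
| 0.2 | 41.0% | 5.6% |
| 0.3 | 77.2% | 4.4% |
| 0.5 | 98.6% | 5.4% |

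Repeat runs with other random seeds gave 39% to 42%, 71% to 74% and 99% for Fisher at d = 0.2, 0.3 and 0.5, and 3% to 6% for the adjusted test.

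**Step 4: different assumptions.** Gamma baseline SDAI (mean 20 or 25, SD 12), factor prevalence 50%, equal proportional effect in both levels, 400 data sets per setting:

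| Mean SDAI | N | Baseline gap | Fisher | Fisher without baseline remitters | Adjusted |
|---|---|---|---|---|---|
| 20 | 1000 | 2 points | 22% | 18% | 5% |
| 20 | 1000 | 4 points | 68% | 60% | 4% |
| 20 | 3000 | 2 points | 53% | 45% | 6% |
| 20 | 3000 | 4 points | 98% | 97% | 5% |
| 25 | 1000 | 2 points | 17% | 18% | 5% |
| 25 | 1000 | 4 points | 46% | 44% | 4% |
| 25 | 3000 | 2 points | 32% | 30% | 4% |
| 25 | 3000 | 4 points | 90% | 88% | 4% |

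**Step 5: real differences (mean SDAI 25).** With equal baselines and Month-6 SDAI truly 20% lower in one level, Fisher flags 68% (N = 1000) and 99% (N = 3000). With a 15% stronger effect but a baseline 4 points higher, it flags only 6.5% (N = 3000), close to the 5% expected by chance.

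**Step 6: role of baseline remitters.** In the main scenario P(baseline ≤ 3.3) = Φ[(ln 3.3 − ln 22)/0.6] = 0.08%, about 2 of 2500. Dropping them leaves the rejection rate almost unchanged, as the fifth column of Step 4 also shows when they are up to 2.4% of patients.

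**The case against.** **Stated aim.** The Protocol objective reads "Occurrence of adverse reactions, factors that may potentially affect safety, and effectiveness". Its punctuation ties factors to safety, with effectiveness a separate item, and Protocol 8.3 places factor evaluation under safety. SAP 8.2.4.3 is headed only as a subgroup analysis and does not claim to find modifiers of drug effect. This stands: the objective is no basis for the point. The basis is that the SAP itself lists backgrounds considered for efficacy and orders tests between their levels.

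**Exploratory status and other analyses.** SAP Section 4 declares all tests exploratory, and no decision rests on these. Changes in SDAI, CDAI and DAS28, and the EULAR response, are planned. This lowers the weight of the point. It does not cure the factor tests, because those analyses are run overall and by average actual daily dose, not across the 11.1.4 factors.

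**Redaction.** A blacked-out block follows 8.2.4.3, and 8.1.3 allows for a logistic model. An adjusted analysis may exist there, so absence of adjustment can be asserted only for the visible text.

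**Stronger readings a reader might infer.**
- That a flagged factor reflects starting activity and not response. Step 5 contradicts this: the test responds to both.
- That counting patients already in remission is the main fault. Under these assumptions it contributes little. The documents give no share of such patients. It could be larger if many came from trials or other hospitals, whose start date (Protocol 6.4) may fall when they are already on drug.
- That the baseline-activity rows must reject even if the drug does nothing. A no-effect scenario with a wider baseline spread (log-SD 0.75) rejected for the SDAI categories in every run. It was set up separately and does not extend to all baseline-activity factors. That starting activity predicts later activity is also ordinary prognostic information.
- That adjustment would reveal a change in drug effect. Effectiveness has no control group (Protocol 8.2), so even an adjusted test shows only association with remission on drug.

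**Conclusion.** The point holds as a minor improvement to the visible text. The tests named for 8.2.4.3 do not adjust for baseline SDAI, so they mix starting activity with response. Under the main scenario, a factor unrelated to response with a 0.2 to 0.5 SD baseline shift is flagged in about 40% to 99% of data sets, against about 5% after adjustment. Masking is also possible.

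The direction held in every scenario tried with a baseline gap. The size depends on assumed values for the number of patients, the baseline distribution, the spread of response and the link between factor and baseline, none of which the documents give. With a 0.1 SD shift the excess is modest (14%), and with no shift there is none.

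**What to change.** In SAP 8.2.4.3:

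1. Test each factor with the logistic model already named in 8.1.3, with baseline SDAI as a continuous covariate. This is the main remedy.
2. Keep the crude remission proportions by factor level as description.
3. Show the baseline SDAI, CDAI and DAS28 rows as descriptive or prognostic, without a test.
4. Word findings as association with remission on Xeljanz, not as a change in drug effect.
5. As a secondary refinement, also report remission among patients with baseline SDAI above 3.3.

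If the redacted block already holds such a model, a cross-reference in 8.2.4.3 that makes it the basis for the tests would do.

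The cost is SAP wording and one model per factor on data already collected. The downside is that patients without a baseline SDAI drop out of the adjusted tests. They remain in the crude table, and their number should be shown beside each test.
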